From LIFE-Pilot, the SD of 400 m walk speed in IL-6 eligible participants is 0.21 m/s, with high correlation ($r > 0.80$) between baseline and 12 month measures. With at least 60 and 75 participants per group (for pairwise comparisons), we project to have >99% power to detect a difference in means of >0.095 m/sec using a one-sided test at the 10% level (a substantial meaningful change).¹⁹² There is also 67% power to detect a >0.038 m/sec difference (a small meaningful change). Using groups of 135 and 165 (for main effects), we would have >99% power to detect >0.095 m/sec, and 86% power for a difference >0.038 m/sec in walking speed. This analysis uses linear mixed models, as for IL-6; a similar approach is used for the secondary outcomes of SPPB, frailty, and grip strength. This achieves the last part of Aim a (i). For people who are unable to complete the 400m walk, we will use their walking speed from the portion completed.

6.10.c. Associations between inflammation and function

We base our calculation of detectable SPPB effects on LIFE data. The correlations between baseline and 24 month follow-up SPPB outcomes were 0.49 (Successful Aging: SA) and 0.47 (Physical Activity: PA); we assume a correlation of 0.5 between baseline and 12 month in ENRGISE. Estimated standard deviations at 24 months were 2.60 (SA) and 2.47 (PA); we assume 2.5. Under these assumptions, for the comparisons of 60 to 65 people, we have 90% power to detect a difference of at least 0.99 SPPB units; for the comparisons of 135 to 165 people, we have 90% power to detect a difference of at least 0.66 SPPB units. Both assume 1-sided tests at the 10% level.

We will examine the relationship between the change in IL-6 and the change in walking speed using univariate regression. Assuming we assess ≥ 285 participants (of 300, $\geq 95\%$) at 12 months, we have 80% power to detect a correlation less than -0.126 (i.e. at least 1.59% of explained variability) using a one-sided test at the 10% level. We have 90% power if the correlation is less than -0.152 (Aim a (iii)).

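### The 86% main-effect power for walking speed cannot share assumptions with the 67% pairwise power beside it; the stated inputs give about 90%

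*Combined protocol and SAP*

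**What the plan says.** Walking speed on the 400 m walk is one of the pilot's two main outcomes (section 6.7.a). Its power paragraph in section 6.10.b gives these inputs:

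- From LIFE-Pilot, "the SD of 400 m walk speed in IL-6 eligible participants is 0.21 m/s", with a correlation above 0.80 "between baseline and 12 month measures".
- A one-sided test at the 10% level.
- 60 and 75 participants for pairwise comparisons: "There is also 67% power to detect a >0.038 m/sec difference (a small meaningful change").
- "Using groups of 135 and 165 (for main effects"): "86% power for a difference >0.038 m/sec in walking speed".
- "This analysis uses linear mixed models, as for IL-6". The IL-6 model, described just before, is adjusted for the baseline value and for strata, and the IL-6 power calculation assumes 5% loss to follow-up.

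No residual SD or loss rate is printed for walking speed.

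**The concern.** Two powers for the same difference and the same test differ only through sample size, so either one determines the other. Here they disagree by more than rounding allows, which means at least one of them is wrong or rests on an assumption that is not stated.

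Section 6.10.b makes the marginal comparison of each drug with placebo its primary focus, with the aim of ruling out small effects. The 86% is the stated power for a small meaningful change on that comparison. A reader interpreting a null walking-speed result would rely on it and needs a figure that can be traced to the inputs.

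**Working it through.** **Method.** Power = Φ(δ/SE − 1.2816), with SE = σ·√(1/n₁ + 1/n₂). The value 1.2816 is the one-sided 10% critical value. For 5% loss, both group sizes are multiplied by 0.95.

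**1. Is this the plan's own method?** For IL-6, section 6.10.b gives a root mean squared error of 0.52, log differences of 0.1054, 0.1625 and 0.2231, and 5% loss.

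| Groups | Stated | Recomputed |
|---|---|---|
| 135 vs 165 | 66 / 91 / 99% | 66.3 / 91.0 / 99.0% |
| 60 vs 75 | 44 / 68 / 87% | 44.4 / 68.3 / 87.1% |

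All six agree. The convention is a simple two-group comparison on pooled counts with 5% loss.

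**2. Walking speed from the stated inputs.** The baseline-adjusted residual SD is 0.21·√(1 − 0.80²) = 0.126, and δ = 0.038.

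| Groups | Loss | SE | δ/SE | Power | Stated |
|---|---|---|---|---|---|
| 60 vs 75 | none | 0.02182 | 1.741 | 67.7% | 67% |
| 60 vs 75 | 5% | 0.02239 | 1.697 | 66.1% | 67% |
| 135 vs 165 | none | 0.01462 | 2.599 | 90.6% | 86% |
| 135 vs 165 | 5% | 0.01500 | 2.533 | 89.5% | 86% |

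The 67% is reproduced; the 86% is not. The stated figures of more than 99% for 0.095 m/s are also reproduced.

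**3. A check that needs neither SD nor correlation.** The ratio of the two standard errors is √[(1/60 + 1/75)/(1/135 + 1/165)] = √(74.25/33.33) = 1.492.

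- From 67% pairwise: (0.440 + 1.282) × 1.492 − 1.282 = 1.288, so main-effect power is 90.1%. Rounding of the 67% (66.5 to 67.5%) gives 89.7 to 90.5%.
- From 86% for main effects: (1.080 + 1.282)/1.492 − 1.282 = 0.301, so pairwise power is 61.8%. Rounding (85.5 to 86.5%) gives 61.3 to 62.4%.
- Taking 5% loss for the main effects only, 67% pairwise still implies 88.9%.

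**4. What would give 86%?** The residual SD would have to be 0.1386 (no loss) or 0.1351 (5% loss). In a baseline-adjusted analysis that means a correlation of 0.75 to 0.77, below the stated lower limit of 0.80. A higher correlation moves the other way: 0.85 gives 94.6 to 95.3%.

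**5. The stratum-adjusted basis.** At the Table 6.1 sizes, stratum 1 has no one assigned to losartan and stratum 2 no one assigned to ω-3. Once strata are in the model, direct information on losartan comes from stratum 2 (45 vs 30) and stratum 3 (90 vs 60): 45·30/75 + 90·60/150 = 18 + 36 = 54. The pooled counts give 135·165/300 = 74.25. By symmetry, ω-3 has the same 54. Fitting the eight Table 6.1 cells gives 53.3 with the other drug in the model, and 51.7 with the interaction also fitted and the drug's effect averaged equally over the other drug. Power is Φ(δ·√(0.95 × information)/σ − 1.2816) with 5% loss.

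| Model | Walking speed, 0.038 m/s | IL-6, 10 / 15 / 20% difference |
|---|---|---|
| Strata and both drugs | 80.7% | 56.4 / 82.7 / 96.2% |
| Adding the interaction | 79.7% | 55.5 / 81.8 / 95.8% |

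So 86% lies between the two bases and matches neither.

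**The case against.** The best rescue is an unadjusted change score. Its SD is 0.21·√(2 × 0.20) = 0.1328, and with 5% loss it gives 86.9% for 135 vs 165. That is close enough to suggest that the two figures were computed under different assumptions. It is not the planned baseline-adjusted analysis, however, and it gives 62.9% for 60 vs 75, so it does not save the pair. It does justify letting the sponsor state the assumption used instead of only replacing the number.

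It can also fairly be said that little depends on this. On the stated counts the printed figure is conservative, a correlation above 0.80 would raise power further, and the sample size is not threatened. That stands.

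A reader might infer that the stated power is simply too high and should be lowered to about 81%. The documents do not support that as the correction. The paragraph names 135 and 165 as its basis, and the IL-6 powers use the same pooled counts. Changing walking speed alone would put the two main outcomes on different bases. The 80–81% also depends on which contrast defines the main effect, and on stratum sizes that section 6.1 says are no longer fixed since the upper limit on stratum 1 was lifted.

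A reader might also infer that this figure decides whether a small change is pursued in the main trial. The decision inputs listed in section 6.10.e do not include a test of 0.038 m/s or its power.

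**Conclusion.** The concern holds as an arithmetic inconsistency. The 67% and 86% cannot come from the same assumptions, and that conclusion needs no SD or correlation, only a common loss rate. The stated inputs identify 86% as the figure that fails. With a correlation of 0.80 and baseline adjustment, 135 vs 165 gives 89.5% with 5% loss and 90.6% without, so 86% understates power by 3.5 to 4.6 points on the plan's own method.

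The stratum issue is separate and affects both main outcomes. It lowers main-effect power to about 80–81% for walking speed and about 56/82/96% for IL-6, assuming 5% loss, the Table 6.1 sizes and the contrasts described above. Whether 86% is too low or too high therefore depends on the basis chosen, but it is not right on either. Neither basis shows that the pilot's sample size is inadequate for its stated purpose.

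**What to change.** In the walking-speed paragraph of section 6.10.b, replace 86% with about 90% (89.5% with 5% loss), and state the residual SD of 0.126 m/s and the loss rate used. Alternatively, keep 86%, state the assumption that produces it, and recompute the pairwise 67% under that assumption. Either way this is a change of one or two numbers and one sentence, and no design feature changes.

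If the sponsor prefers to report the power of the stratum-adjusted model, the main-effect contrast and the stratum counts should be defined, and the IL-6 main-effect powers moved to the same basis along with walking speed. The SPPB detectable difference for 135 vs 165 in section 6.10.c would then need the same treatment. That costs a short recalculation and somewhat lower stated powers.

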are generally pro-inflammatory,⁵⁸ and can cause a decline in muscle protein synthesis via ER stress.⁵⁹ ω -3 supplementation down-regulates inflammation⁶⁰ in part through decreased TNF- α expression and ω -3 fatty acids are likely to improve mTOR signaling, thereby stimulating muscle protein synthesis in humans.⁶¹ A meta-analysis of several RCTs has shown that ω -3 reduce both IL-6 and CRP in chronic non-autoimmune disease.⁶²

ARBs are primarily indicated for the treatment of hypertension. The ARB LO is also a partial PPAR- γ agonist,⁶³ yielding potent anti-inflammatory effects.⁶⁴ LO reduces IL-6 in human⁶⁵ and animal studies,⁶⁶ possibly through PPAR- γ /AMPK agonism, blockage of proinflammatory angiotensin II AT1 signaling, or both.^{64, 67} ARBs mitigate lipopolysaccharide -mediated inflammation, and inhibit TNF- α -mediated endothelial Receptor for Advanced Glycosylation Endproduct (RAGE) expression.⁶⁸ LO has been shown to improve skeletal muscle related activity measures in older mice.^{66, 69} In summary, inflammation plays a major role in the loss of physical function through a wide variety of mechanisms, many of which offer interventional targets.

All drugs have multiple effects. LO^{63, 67, 70} and ω -3,^{71, 72} in addition to averting inflammation, also affect vasculature, coagulation, metabolism, and skeletal muscle, all of which may benefit mobility (Figure 5.1.). Testing these two different interventions that avert inflammation may provide added support regarding the relevance of their common anti-inflammatory effect in possibly benefiting walking speed and ultimately mobility.

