- Testing LO and ω -3 in combination to maximize their effects on inflammation and mobility
- The use of several adaptive features in design and stratified screening for ENRGISE pilot study

Table 5.2. Summary of selection criteria and candidate interventions (see details in the text)

Interventions	Criteria	1. Safe, tolerable, acceptable	2. IL-6 reduction	3. Physical performance	4. Innovation	5. Mechanism	6. Practical, affordable
ACEIs, ARBs		+	+	+	+	+	+
ω -3		+	+	+	+	+	+
Mediterranean diet		+	+	+	+	+	-
Physical activity, weight loss		+	+	+	-	+	+?
Vitamin D		+	+	+	-	+	+
Anti-TNF- α , -IL6, -IL1; methotrexate thiazolidinediones		-	+	?	+	+	?
Statins, chloroquine, colchicine		-	+	-?	+	-	+
Corticosteroids, aspirin, NSAIDs, cox-2 inhibitors		-	+	?	+	+	+
Metformin, fosinopril, ghrelin, lactoferrin, oxytocin, salsalate, curcuma, creatine, probiotics, resveratrol		+	-?	-?	+	+?	+

+ positive evidence, - negative evidence, ? evidence lacking

- The assessment of novel inflammatory markers in ENRGISE pilot study

6. Research Plan

6.1. Design. We test LO, ω-3 and their combination in a double-blind, placebo-controlled RCT (The ENRGISE Pilot Study). Randomization is concealed via the secure web-based data management system. We use a permuted block algorithm (with random block lengths).

LO and ω-3 are considered safe in elders.^{80-84, 148, 149} We conduct this pilot RCT to (a) decide whether we should proceed to the main ENRGISE trial with 1 or 2 interventions, and (b) if two interventions are warranted whether we should proceed as a three-arm (without the combination group) or a 2x2 factorial study. The pilot is designed to achieve the following goals: (1) estimate recruitment yields including percent consenting; (2) confirm safety and tolerability; (3) assess the impact of interventions on IL-6 and walking speed as well as the secondary outcomes of Short Physical Performance Battery (SPPB), frailty, and muscle strength; (4) evaluate the strength of relationship between the change in IL-6 with the change in walking speed; (5) allow selection of the interventions that demonstrate high participant compliance and retention; (6) collect data on outcomes of major mobility disability and other mobility measures; (7) support the decision to proceed with a factorial or parallel design; (8) examine intra-subject variability of IL-6; (9) explore the impact of the interventions on

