- The participant is diabetic and fasting glucose > 300 ,
- Baseline LDL > 130 AND increases by $\geq 20\%$ from baseline,
- The participant is taking a blood pressure lowering agent OR is also participating in the Losartan arm of the study AND blood pressure is $<90/50$, or
- Participant does not tolerate the fish oil.

The principal investigator/study physician at each site has the discretion to opt out of ω -3 fish oil dose adjustments due to glucose and/or LDL levels.

We increase the dose of ω -3 fish oil to 2.8 g/day if the average of IL-6 measured at 3- and 6-month visits has not **decreased by at least 40%** vs. baseline (average of screening visits 1 and 2). The 40% threshold is selected based on previous trials with ω -3 fatty acids. ω -3 fatty acids have been shown to reduce IL-6 by $>50\%$ in RCTs^{75, 76} and to be consistent with the threshold used below for losartan. To minimize the impact of outliers due to acute illness, the 3-month or the 6-month IL-6 measure are excluded or postponed if there is an acute illness within one month prior to the visit. In the rationale for dose titration we use the following assumptions:

1. IL-6 biovariation as a CV is $\sim 30\%$. This is a reasonable estimate based on our own estimates (unpublished data) and those of others.^{150, 151} This means that a SD of each person's day to day variability is about 30% of the mean value.
2. We have two measures at baseline that can be averaged to yield a reasonable estimate of each person's average value.
3. For dose adjustment we use IL-6 measured at 3 months and 6 months.
4. The half-life of IL-6 is extremely short (<30 minutes), so response to interventions is essentially coincident to the effect of the interventions.
5. We screen for outliers by excluding participants who experienced an acute illness within a month of the visit

6.2.b. LO and placebo (cellulose based) are obtained in 25 mg and 50 mg capsules. The shell capsules are cellulose based. Placebo and LO have identical shape, color, taste and weight. We start with 25 mg/day, if tolerated, we step up to 50 mg/day. If there are no safety concerns, we continue with 50 mg/day until the 6 month visit. If the average of IL-6 measured at 3- and 6-month visits does not **decrease by $\geq 40\%$** vs. baseline (average of screening visits 1 and 2), we increase the dose to 100 mg/day. Equivalent doses of ARBs have shown to reduce IL-6 by $>40\%$ ^{77, 78} and by 58% ⁷⁹ in RCTs.

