6.10 Data analyses and power for the ENRGISE Pilot Study and biomarkers assays

The data analyses and power section is presented in the order by which the aims are likely to be achieved rather than the order in which the aims are stated elsewhere in the protocol.

6.10.a. Feasibility and recruitment

Feasibility of recruitment and identifying the study population are contained in Aim a (ii). In the ENRGISE Pilot Study we will use one-sided tests/confidence intervals because we wish to rule out conditions that would make the main study infeasible. Having a higher than hypothesized safe tolerable rate, higher yield for recruitment, or stronger relationship between the changes in IL-6 and walking speed would simply make the follow-up study easier to implement. For efficacy, we use tests at the 10% significance level;^{187, 188} this is consistent with the FDA's aims for phase 2 versus phase 3 studies.^{189, 190} No formal adjustment for multiple comparisons is planned for the pilot study.

We assess the recruitment yields in strata 1-3 presented in Table 6.1 and the proportions of people who tolerate LO and ω -3. One-sided exact confidence intervals of these proportions are calculated. If we need to screen 300 people to recruit 75 into strata 1 (People not using ω -3) or 2 (People not using ACEI or ARB) (25% yield), the 95% one-sided CI would set the lower bound of our recruitment yield at 20.9% using a Clopper-Pearson interval¹⁹¹ and 8.3% if we need to screen 750 (10% yield). For stratum 3 (People not using ACEI, ARB, or ω -3) (target 150), these lower limits would be 22.1% (25% yield) or 8.8% (10% yield). Note that those eligible for stratum 3 are also eligible for strata 1 and 2; these people are also used to estimate the

proportions eligible; thus, our CIs above are conservative.

6.10.b. Intervention Effect

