We use the "intention to treat" approach assuming participants are grouped according to randomization for all analyses of the intervention effect. The stratified recruitment and randomization allow us to compare mean log(IL-6) between each of the three active groups to placebo using a linear mixed model with both main effects and their interaction, adjusted for baseline log(IL-6) and strata. Time is a repeated factor, and the primary comparison is based on a contrast at 12 months. The covariance structure will be assumed to be unstructured. The primary focus is on marginal comparisons (135 and 165/group) between each active intervention and placebo using one-sided hypothesis tests at the 10% level (we are not looking for definitive evidence, but to rule out small effects). We assume 5% loss to follow-up (LTFU); this is similar to the 5% we achieved in LIFE. Using the root mean squared error from LIFE-P (adjusted for baseline log(IL-6) and treatment) of 0.52, we have 91% power to detect a difference if the difference (on the log scale) is at least 0.1625. This is equivalent to the difference between 4.20 and 3.57 pg/ml (or a 15% difference). We would have 66% power for a 10% difference (4.20 vs. 3.78 pg/ml, 0.1054 on the log scale) and 99% power for a 20% difference (4.20 vs. 3.36 pg/ml, 0.2231 on the log scale). Individual treatment group comparisons (at least 60 vs. 75/group) would have 44% power for a 10% difference, 68% power for a 15% difference, and 87% power for a 20% difference. This achieves the first part of Aim a (i). As sensitivity analyses, we also explore the impact of additional factors (e.g., diet, physical activity, medication use) by adding these factors to the models. Although the mixed model is robust against data missing at random (MAR), multiple imputation will be used in sensitivity analyses.

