To assess intra-person variability in IL-6 (Aim a (iii)), we measure IL-6 at both screening visits. We use a Bland-Altman plot to assess agreement; this is summarized using a 95% CI of the difference at the two visits providing information on the expected differences over one week due to biological variability and measurement error. If agreement is high, one measure is likely sufficient for recruitment into the main study. If not, we may need to use two or more measures to determine eligibility and to assess participant-specific risk.

6.10.d. Additional inflammatory biomarkers:

In addition to IL-6 levels, we examine additional markers of inflammation (Aim b (i) and (ii)). As with IL-6, our primary focus is on the relationships between changes in cytokines with the change in walking speed using linear mixed models. We use stratified linear mixed models (as described above for IL-6) to examine the impact of interventions on these cytokines. These analyses assess whether changes in these cytokines are of similar magnitude to IL-6. As the absolute levels differ between cytokines, focus is on relative changes from baseline. We also examine these cytokines in models also including baseline and follow-up log(IL-6) to assess whether they provide additional predictive information. We also explore MMD event rates by baseline levels of IL-6 and additional cytokines to explore whether we can use an additional cytokine to select a population at greater risk to use for the main study, recognizing the potential tradeoff between ease of recruitment and selecting a population at higher risk.

6.10.e. Informing the main study

We assess compliance and retention rates (Aim a (ii)). Although we expect to be underpowered for incident mobility disability, we collect these data and compare estimates of event rates to those obtained in SA group LIFE participants that would have been eligible for ENRGISE (Aim a (ii)). While power is limited, we also examine whether there is sub-additivity and interaction of interventions in stratum 3, which supports the decision of whether to proceed with a factorial or parallel group design in Phase 3 (Aim a (ii)). .

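### The IL-6 change versus walking-speed change analysis is specified only as a pooled univariate regression; an arm- and stratum-adjusted regression, led by month 6, should be prespecified beside it

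*Combined protocol and SAP*

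**What the plan says.** - Section 6.1 lists as goal 4 to "evaluate the strength of relationship between the change in IL-6 with the change in walking speed".
- Section 6.10.c gives the method: "We will examine the relationship between the change in IL-6 and the change in walking speed using univariate regression". It states 80% power at a correlation of -0.126 and 90% at -0.152, one-sided at 10%, with at least 285 people at 12 months. No arm, stratum or baseline term is named, and the scale of the IL-6 change (raw or log) is not given.
- Section 6.10.d, on the other biomarkers, says: "As with IL-6, our primary focus is on the relationships between changes in cytokines with the change in walking speed using linear mixed models". This may imply a second model for IL-6, but no terms are listed. The next sentence, on stratified mixed models, concerns only the effect of the interventions on the cytokines.
- Section 6.10.b does carry arm and stratum, but for the treatment comparison: "a linear mixed model with both main effects and their interaction, adjusted for baseline log(IL-6) and strata".
- Section 5 says that the two drugs "also affect vasculature, coagulation, metabolism, and skeletal muscle, all of which may benefit mobility".
- Section 6.10.a remarks that a "stronger relationship between the changes in IL-6 and walking speed would simply make the follow-up study easier to implement". Section 6.10.e makes the relationship one of several inputs to the main-trial decision.

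**The concern.** A pooled regression over four randomised arms mixes two sources of covariation: the association among people within an arm, and differences between arm means. If a drug shifts both IL-6 and speed, the arm means line up on a negative slope whether or not IL-6 has anything to do with speed.

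The motivating hypothesis in section 5 is that lowering IL-6 improves mobility. A negative pooled correlation could be taken as support for that link when it shows only that a drug moved both outcomes. Section 6.10.a plans no caution for a strong result. No section specifies an arm-adjusted version, and 6.10.c and 6.10.d name different model classes without reconciling them.

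**Working it through.** **1. The plan's own figures.** Fisher z, n = 285, one-sided 10% (critical value 1.2816):
- r at 80% power = tanh((1.2816 + 0.8416)/√282) = 0.1258
- r at 90% power = tanh((1.2816 + 1.2816)/√282) = 0.1515

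These match the stated 0.126 and 0.152. The power statement is correct for the analysis it describes.

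**2. Pooled correlation with zero within-arm association.** Inputs:
- Table 6.1 numbers: 90 / 75 / 75 / 60. So 135 of 300 (0.45) receive a given drug. The number of active drugs is 0, 1 or 2 with proportions 0.3, 0.5 and 0.2.
- Effects per drug: 15% lower IL-6 (0.1625 on the log scale, 6.10.b) and 0.038 m/s (6.10.c). That the speed effect arises by a route other than IL-6 is an assumption; the documents do not quantify one.
- SD of log IL-6 change: 0.52. In 6.10.b this is a residual SD adjusted for baseline, so it is a proxy. With equal variances at the two times, residual SD / change SD = √((1+ρ)/2) ≤ 1, where ρ is the baseline-to-follow-up correlation, so 0.52 is likely at the lower end. I also use 0.70 (assumed).
- SD of speed change: 0.21 × √(2(1−0.80)) = 0.133 m/s. Section 6.10.c says the correlation exceeds 0.80, so I also use 0.90 (assumed).

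Let V be the variance of the number of active drugs that have an effect. Then

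r = −(0.1625 × 0.038 × V) / √[(SD_IL6² + 0.1625²V)(SD_speed² + 0.038²V)]

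and the rejection rate is Φ(atanh|r| × √282 − 1.2816).

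- One drug: V = 0.45 × 0.55 = 0.2475. r = −0.001528 / √(0.2769 × 0.01800) = −0.022. Rate Φ(0.364 − 1.282) = **18%**.
- Both drugs, additive: V = (0.5 + 4 × 0.2) − 0.9² = 0.49. r = −0.003026 / √(0.2833 × 0.01835) = −0.042. Rate Φ(0.705 − 1.282) = **28%**.

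| Assumption | One drug | Both drugs |
|---|---|---|
| IL-6 SD 0.52, speed r 0.80 | 18% | 28% |
| IL-6 SD 0.70, speed r 0.80 | 16% | 22–23% |
| IL-6 SD 0.52, speed r 0.90 | 22% | 38% |

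Simulation with Table 6.1 strata and weights (20,000 trials per scenario) agrees. With both drugs, but the combination no better than one drug, it gives 17%. When the drugs move IL-6 only, speed only, or one outcome each, the pooled test rejects 9.4–10.0%.

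**3. Adjusted test.** With LO, omega-3, their interaction and two stratum indicators, the change-on-change test rejects 9.4–10.5% in all of these scenarios. Five terms leave n − 3 − 5 = 277. Power at r = −0.126 moves from 80.1% to 79.6%, and the detectable correlations become 0.127 and 0.153.

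**4. The dose step.** Section 6.2.a.1 states: "For dose adjustment we use IL-6 measured at 3 months and 6 months". After month 6, therefore, dose depends on each person's own IL-6 change, and arm terms cannot absorb that. In simulations with a CV of 30% (6.2.a.1), an assumed between-person log SD of 0.5 and effects of 15% / 0.038 m/s:
- If the step adds nothing further, the 12-month adjusted test stays at about 10% under the null.
- If the step adds an assumed 50–100% to both drug effects, that test becomes conservative (about 2–7%). Its power for a true within-arm link near r = −0.126 falls to about 73–66% (one drug) or 64–51% (both drugs).
- The month-6 version keeps 9–11% under the null and about 78–80% power.

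**5. Attenuation.** A CV of 30% gives a log variance of ln(1.09) = 0.0862. One follow-up value against a two-measure baseline carries 1.5 × 0.0862 = 0.129, which is 48% of 0.52². An observed r of −0.126 then needs a true r of about −0.126/√0.52 = −0.17.

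**The case against.** The strongest reply is that the plan contains no error. It promises to evaluate the strength of a relationship and claims neither mediation nor a within-arm effect. In the scenarios above the marginal correlation really is negative, so rejecting is correct. That stands. A reader might infer that the pooled test is invalid or has a broken error rate; the documents do not support this, because the excess arises only against a within-arm null that 6.10.c never states. If all drug benefit ran through IL-6, the between-arm part would be genuine signal.

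A reader might also infer that the main-trial decision would be misled. Section 6.10.e lists several inputs and sets no threshold on this one, and the randomised comparisons in 6.10.b and 6.10.c estimate each drug's effect directly. Much higher pooled rates are possible (46% for one drug, 82% for both, at 20% and 0.095 m/s). They need the plan's substantial speed effect to arise entirely by another route, so they are extremes.

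Section 5 offers a partial answer: "Testing these two different interventions that avert inflammation may provide added support regarding the relevance of their common anti-inflammatory effect". Agreement between two different drugs helps, but it does not separate the explanations inside a regression that pools them.

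Finally, the adjusted slope does not settle mechanism either. It is observational, and noise weakens it. That also stands, and it limits what the adjusted result may be used for. What survives is that the pooled result alone leaves goal 4 ambiguous.

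**Conclusion.** The point holds as a cheap improvement of low to moderate severity. The only specified and powered analysis of goal 4 cannot tell an IL-6/speed association within arms from a drug that moves both outcomes, and the protocol itself raises the second possibility. At modest assumed effects the one-sided 10% pooled test rejects about 18% (one drug) or 28% (both), within about 16–22% and 22–38% over the variances tried.

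These figures rest on an assumed non-IL-6 effect on speed and on 0.52 standing in for the SD of change; the documents give neither quantity. The plan's power figures reproduce. Whether 6.10.d already intends an adjusted IL-6 model cannot be determined from its wording.

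**What to change.** - Keep the pooled regression in 6.10.c.
- Beside it, prespecify a regression of change in walking speed on change in log(IL-6), with LO, omega-3, their interaction and stratum as terms and no baseline levels as covariates, tested one-sided at 10%.
- Report it for baseline-to-month-6 and baseline-to-month-12 changes, with month 6 as the lead adjusted result because it precedes the IL-6-driven dose step. Table 6.3 marks IL-6 and physical performance at month 6; this assumes that the 400 m walk is among those measures.
- Report pooled and adjusted results together. State that a negative pooled correlation alone is not evidence of a link beyond shared drug effects, and that a null adjusted result is not evidence of no link.
- In 6.10.d, say whether the comparison with IL-6 refers to one of these models, and list its terms.

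The cost is SAP wording, with no new data. The added terms alone take about half a point of power, but the 12-month adjusted version can lose much more if the dose step strengthens the drug effects. The adjusted slope remains a within-arm, observational and attenuated estimate that does not show mediation.
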